## PROTOCOL SUMMARY

Aortic stenosis (AS) is the most common primary valve disease leading to surgery or catheter intervention in Europe, with a growing prevalence due to the aging population. Severe AS is associated with significant morbidity and mortality and is treated by surgical valve replacement (SAVR) or transcatheter aortic valve implantation (TAVI). However, significant coronary artery disease (CAD) is reported in more than 60% of patients with AS, and this concomitant CAD needs to be correctly assessed because untreated significant CAD is associated with adverse outcomes. Current guidelines recommend intra-coronary pressure measurement using either fractional flow reserve (FFR) or non-hyperemic pressure ratios (NHPR) for the assessment of intermediate coronary artery lesions before revascularization. However, correctly identifying hemodynamically significant coronary stenoses by FFR or NHPR is difficult in patients with AS because of the hypertrophic remodeling related to the valve pathology, which interferes with coronary blood flow in the microcirculation and reduces the accuracy of FFR and NHPR. This has resulted in substantial controversy in this field of coronary artery disease and there is currently no clear guideline for the management of AS patients with concomitant CAD. Recent technological advances now permit the concomitant evaluation of FFR/NHPR and microcirculatory function at the time of cardiac catheterization. Using this technology, we will simultaneously evaluate the hemodynamic significance of coronary stenoses (using FFR and a NHPR - Resting Full cycle Ratio [RFR]) and the microcirculatory function (Index of Microcirculatory Resistance, IMR) in patients with AS and CAD prior to SAVR/TAVI. One hundred patients with AS and intermediate CAD will be included in the study. Of them Eighty will undergo AVR and at least 58 will undergo the follow-up at 6 Months. During routine pre-valve replacement cardiac catheterization, measurement of intermediate CAD lesions (by FFR and RFR) and IMR will be performed in duplicate using new software. These measures of CAD severity will be compared with a gold standard non-invasive test (single photon emission computed tomography [SPECT]). This will validate the use of RFR and determine if IMR can be used to improve the ischemia prediction of FFR. In addition, the patients undergoing TAVI the LVEDP will be measured immediately before and after valve implantation and FFR, RFR and IMR will be measured after valve implantation. Subsequently, when these patients undergo a post-intervention (whether SAVR or TAVI) evaluation 6 months after valve replacement, the effect of valve replacement on FFR, RFR and IMR (again in duplicate) will be determined. This will be the first study measuring these parameters before and 6 months after valve replacement. The data will be used to calculate a 'corrected' FFR (or RFR) based on microcirculatory function in these patients, which can then be used in the future to correctly evaluate CAD pre-intervention in patients with AS. This will translate into more efficient management of patients with AS. Fewer of these patients will unnecessarily undergo coronary artery bypass grafting or stenting when the CAD does not need to be treated and, conversely, in those who do require treatment of the CAD, revascularization can be carried out during a single surgery/intervention, avoiding multiple high risk procedures in patients who are already at high peri-operative/peri-interventional risk.

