AS and intermediate CAD. They determined that the optimal iFR threshold for detecting ischemia compared with  $^{99m}\text{Tc}$  single-photon emission computed tomographic (SPECT) myocardial perfusion imaging was 0.82, while the cut-off for FFR was 0.83. This is in contrast to the large, outcome-based randomized controlled studies in patients without AS, and different to the current guideline cut-offs of  $\leq 0.89$  for resting indices and  $\leq 0.80$  for FFR. The RFR threshold for detecting ischemia has not yet been determined in patients with AS.

A more comprehensive study with performance of intra-coronary measurements before and after TAVI may help determine the effect of adverse LV remodelling and microvascular dysfunction on the hemodynamic measurement of coronary artery lesions in patients with severe AS. However, the timing of the follow-up measurements has not been clearly defined. Several studies have performed acute measurements pre- and post-TAVI but no invasive study (measuring FFR and/or resting indices) has been performed after allowing adequate time for reverse remodelling in order to really determine the effect of microvascular reverse remodelling on intra-coronary hemodynamic measurements. Exactly how long is needed after TAVI to ensure adequate myocardial and microvascular remodelling has occurred in order to appropriately use intra-coronary hemodynamic measurements is not known at this stage. One MRI-based study demonstrated a significant reduction in indexed LV mass from  $76\text{g}/\text{m}^2$  to  $68\text{g}/\text{m}^2$  within a few days. In another study, echocardiographic ejection fraction and LV global longitudinal strain improved significantly when measured 10 days after TAVI. However, indexed LV mass improvement was only significant during long-term (months-to-years) follow up. In a more recent, echocardiographic-based study, indexed LV mass decreased from  $117\text{ g}/\text{m}^2$  to  $100\text{ g}/\text{m}^2$  in a surgical aortic valve replacement (SAVR) group and  $114\text{ g}/\text{m}^2$  to  $108\text{ g}/\text{m}^2$  in a TAVI group after 3 months with further reductions at one year. Whether these global changes in LV remodelling translate into improvements in microvascular function, and hence improve the diagnostic accuracy of FFR is not yet known.

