## Secondary outcomes

- 1. A description of the range of IMR values in a cohort of patients with severe AS will be a novel and important contribution to the field of interventional cardiology. Furthermore, the change in IMR (microvascular function) in response to valve replacement will be an important finding in this study. If there is a significant decrease in IMR then this indicates that microcirculatory function improves 6 months after aortic valve intervention. Since microvascular function predicts outcomes in patients with AS, IMR evaluation at 6 months after TAVI/SAVR might provide an additional method to risk stratify these patients even after correction of the valve pathology.
- 2. If the “corrected” FFR (at baseline; based on baseline IMR) does not correlate with the post-intervention FFR then a correction of FFR using baseline IMR does not improve the accuracy of FFR in patients with severe AS.
- 3. Compared with SPECT, a correlation of FFR and RFR will be an important contribution. Firstly, this will be a validation of RFR as a resting measure of ischemia in AS patients. Secondly, these data will support the data of a previous study with a different resting measure of ischemia (iFR) or the findings may be in conflict with the previous study, which would be important.

4. Using SPECT as a standard of myocardial ischemia, IMR may improve the ischemia prediction of FFR. This would be an extremely important finding, supporting the routine use of IMR in patients with microvascular disease when coronary artery lesions need assessment by FFR. Because AS is an important clinical condition with reversible microvascular dysfunction, this provides an excellent naturally occurring model for the study of microvascular function and CAD. These findings will be useful in other groups of patients who also have microvascular dysfunction (including patients with heart failure, obesity, diabetes, liver disease, chronic kidney disease and heart transplant patients). Being able to factor-in microvascular dysfunction (using simultaneously measured microvascular resistance) at the time of FFR measurement will permit accurate assessment of the severity of CAD in these patients. This study has the potential to revolutionize the assessment of coronary artery lesions, not just in patients with AS, but in all patients with CAD since the validity of CAD assessment by FFR/NHPRs may, indeed, depend on microvascular function.

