## 9. STATISTICS AND ANALYSIS

### 9.1 Sample Size

The sample size for the ***primary objective*** (change in FFR after aortic valve intervention) is based on previous measurements of FFR in patients with aortic stenosis, where a standard deviation of the data was reported. An expected mean FFR of 0.82 with a standard deviation of 0.08 was used in the calculation. Fifty eight (58) patients with pre- and post-interventions catheterizations will be sufficient to detect a reduction in the FFR from 0.82 to 0.79 with an alpha level of 0.05 and power of 0.80. A total sample of 100 patients with baseline measurements of which 80 patients will undergo (T)AVR without revascularisation (20% will undergo revascularisation) and in this way are eligible for pre-and post-intervention catheterization will allow for a 25 % drop-out during the follow-up phase of the study. Missing values will predominantly be at random. Therefore, the primary endpoint will be assessed using complete case analysis. To account for missing values, the number of patients will be increased from 58 to 80 (since missing data will be excluded from analysis).

For the ***secondary objective*** (comparison of FFR versus RFR): approximately 10-20% will have left main CAD, triple vessel disease, prior myocardial infarction or tandem lesions and will not be eligible for SPECT. One Hundred patients with baseline measurements will allow a 20% drop-out to end up with 80 patients with both baseline SPECT and invasive measurements. Yamanaka *et al.* found that a sample of 80 patients was necessary to determine the optimal cutoff value of iFR for indicating myocardial ischemia. Since RFR and iFR have an extremely high correlation (0.99), the same number of patients (80) is expected to achieve an area under the ROC curve of 0.70 with 0.90% power at a significance level of 0.05 in a 2-sided test.

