### 9.2 Statistical analysis

All quantitative variables will be tested for normal distribution according to the Kolmogorov-Smirnov test. Statistical analyses will be performed via the SPSS statistical software package,

applying a significance level of  $\leq 0.05$ . Continuous variables will be expressed as mean  $\pm$  SD. Comparisons will be done with paired t-, Wilcoxon rank signed, Mann-Whitney U- or Kruskal-Wallis test when appropriate. The chi-square test will be applied for categorical variables and results will be expressed as n (%). Analysis will be performed to compare the intra-coronary measurements (FFR, RFR, IMR) prior to intervention (group 1) versus 6 months after intervention (group 2). Descriptive statistics (mean/median, standard deviation and percentiles for continuous data; percentage for categorical data) and graphical representation (boxplots, histograms and density plots) will be used to compare both groups' characteristics. Intra-coronary measurements in both groups will then be compared and tested using statistical tests (paired t-, Wilcoxon rank signed test). The correlation between FFR and RFR will be analyzed using Pearson correlation coefficient. The diagnostic performance of RFR in indicating SPECT myocardial ischemia will be evaluated using receiver operating characteristic (ROC) curve analysis.

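### Section 9.2 fixes no RFR cut-off and plans no internal validation; a cut-off chosen and assessed in the same 80 patients would overstate sensitivity plus specificity by about 0.10 to 0.14 at AUC 0.70

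*Combined protocol and SAP*

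**What the plan says.** The relevant statements are spread over five places in the combined protocol and SAP.

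- **Background (section 1).** It reports that an earlier study in aortic stenosis found optimal cut-offs against SPECT of 0.82 for iFR and 0.83 for FFR. It contrasts these with the guideline values of ≤0.89 and ≤0.80, then adds: "The RFR threshold for detecting ischemia has not yet been determined in patients with AS".
- **Study Objectives, secondary outcome 5.** FFR and RFR are to be compared with SPECT for diagnostic performance, and the results set against that earlier study.
- **Section 9.1.** The earlier study is cited as showing that "a sample of 80 patients was necessary to determine the optimal cutoff value of iFR for indicating myocardial ischemia". The same number is carried over to RFR on the strength of a 0.99 correlation between the two indices, and it "is expected to achieve an area under the ROC curve of 0.70". On enrolment: "One Hundred patients with baseline measurements will allow a 20% drop-out", the aim being "to end up with 80 patients with both baseline SPECT and invasive measurements".
- **Section 9.2.** The whole analysis provision for this aim is: "The diagnostic performance of RFR in indicating SPECT myocardial ischemia will be evaluated using receiver operating characteristic (ROC) curve analysis". No threshold to be tested is named, and no rule for choosing one. There is no split or second sample, no cross-validation and no bootstrap.
- **Protocol Summary and Expected outcomes.** The first says "This will validate the use of RFR and determine if IMR can be used to improve the ischemia prediction of FFR"; the second says "this will be a validation of RFR as a resting measure of ischemia in AS patients".

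**The concern.** A cut-off picked because it performs best in a sample looks better in that sample than it will in new patients. With 80 patients, perhaps 16 to 40 of them ischaemic, the effect is not small. The plan identifies an unknown threshold as the gap, takes its sample size from a study that derived a threshold, and intends to compare with that study. It then leaves section 9.2 silent on how a threshold would be obtained or its accuracy corrected.

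Two results are at stake. One is the sensitivity and specificity reported for RFR in aortic stenosis. The other is the comparison of the RFR threshold with the earlier iFR threshold and the guideline value. Expected outcomes says that agreement or conflict with the earlier study would each be of interest. Without an interval for the cut-off, either could be chance.

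**Working it through.** **Inputs from the plan.** 80 analysed patients, AUC 0.70, two-sided alpha 0.05, and power printed as 0.90% and read here as 0.90 (all section 9.1).

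**Inputs not in the plan, so assumed.** Null AUC 0.50; share of patients with SPECT ischaemia 20 to 50%; index normally distributed with equal SD in ischaemic and non-ischaemic patients (binormal); cut-off chosen to maximise the Youden index J = sensitivity + specificity − 1.

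**Step 1: reproduce the plan's number.** Enrolment: 100 × (1 − 0.20) = 80. For the AUC test with 40 ischaemic and 40 non-ischaemic patients (Hanley-McNeil):

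- SE under the null = √[81 / (12 × 40 × 40)] = 0.0650.
- Under AUC 0.70, the two variance terms are 0.7/1.3 = 0.5385 and 2 × 0.49/1.7 = 0.5765. SE = √{[0.21 + 39(0.5385 − 0.49) + 39(0.5765 − 0.49)] / 1600} = 0.0585.
- Power = Φ[(0.20 − 1.96 × 0.0650)/0.0585] = Φ(1.24) = 0.89.

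So 80 is about right for the AUC if roughly half the patients are ischaemic. At 30% ischaemia the same formula gives power 0.82, and at 20% it gives 0.70. The calculation concerns the AUC only; it says nothing about the precision or bias of a cut-off.

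**Step 2: optimism of a cut-off chosen in the same 80 patients.** In the binormal model the separation between groups is d = √2 × Φ⁻¹(AUC). This is 0.742 SD at AUC 0.70 and 1.812 SD at AUC 0.90. The best achievable J is 2Φ(d/2) − 1, which is 0.289 and 0.635. For each setting I simulated 20,000 samples of 80, took the maximum-Youden cut-off c, and compared the apparent J with the true J at that cut-off, Φ(c) − Φ(c − d).

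| AUC | Ischaemia | Apparent J | True J at chosen cut-off | Overstatement | 95% range of cut-off (within-group SD) |
|---|---|---|---|---|---|
| 0.70 | 20% | 0.398 | 0.261 | 0.137 | 1.92 |
| 0.70 | 30% | 0.382 | 0.265 | 0.117 | 1.77 |
| 0.70 | 40% | 0.373 | 0.266 | 0.107 | 1.69 |
| 0.70 | 50% | 0.370 | 0.267 | 0.103 | 1.68 |
| 0.90 | 20% | 0.710 | 0.608 | 0.101 | 1.34 |
| 0.90 | 30% | 0.697 | 0.613 | 0.084 | 1.22 |
| 0.90 | 40% | 0.693 | 0.615 | 0.078 | 1.16 |
| 0.90 | 50% | 0.691 | 0.615 | 0.076 | 1.14 |

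At AUC 0.70 the overstatement divides into 5 to 11 points of sensitivity (largest when ischaemia is rare) and 3 to 5 points of specificity.

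**Step 3: what the cut-off range means on the RFR scale.** The plan gives no SD for RFR. Borrowing the FFR value of 0.08 from section 9.1 as the within-group SD, the 95% range at AUC 0.70 is 1.7 × 0.08 = 0.14 to 1.9 × 0.08 = 0.15 wide. At AUC 0.90 it is 1.14 × 0.08 = 0.09 to 1.34 × 0.08 = 0.11. The two resting-index thresholds that the Background contrasts differ by 0.89 − 0.82 = 0.07.

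**Step 4: effect of the remedies.** At a cut-off fixed in advance, sensitivity and specificity are ordinary sample proportions and carry no selection bias. Bootstrap optimism correction was simulated at AUC 0.70 (600 samples, 100 resamples each):

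- 30% ischaemia: apparent 0.385, corrected 0.309, true 0.265. The overstatement falls from 0.12 to 0.04.
- 40% ischaemia: apparent 0.370, corrected 0.297, true 0.265. The overstatement falls from 0.10 to 0.03.

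**The case against.** The sentence about an optimal cut-off in section 9.1 describes what the earlier iFR study needed; the sentence after it sizes this study for an AUC. Section 9.2 commits only to ROC analysis. A reader might infer that the plan has declared it will derive an RFR cut-off and report its accuracy in the same patients. No sentence says so, and the supportable criticism is of an omission. Even so, an undetermined threshold, a number borrowed from a threshold-finding study and a promised comparison with that study make derivation the likely course.

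The AUC of a single measured index involves no choice of cut-off, so the quantity the plan is sized for is free of this bias. So are results at the guideline thresholds. Both statements are correct and limit the point to accuracy at a data-chosen cut-off.

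A reader might also take the validation wording as a claim that a derived cut-off has been validated. In both places it refers to RFR as a measure checked against SPECT, which is ordinary usage. Rewording it would be largely editorial, and the point does not depend on it.

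It can further be said that making the guideline cut-offs the main accuracy result would replace the plan's question, which is whether thresholds differ in aortic stenosis. That is fair. Results at fixed cut-offs should stand beside the data-derived one; which leads is a design choice.

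Finally, this is a secondary objective, and section 3.8 leaves revascularisation to the Heart Team in routine practice. The consequence is for what is reported.

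**Conclusion.** The point holds conditionally. It is certain that section 9.2 neither fixes an RFR cut-off nor provides for correcting one chosen from the data. If the cut-off is chosen and assessed in the same 80 patients without correction, sensitivity plus specificity would be overstated by about 0.10 to 0.14 at AUC 0.70 and by about 0.08 to 0.10 at AUC 0.90. The cut-off would also be too imprecise, on the borrowed SD, to tell apart the thresholds the Background contrasts.

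These sizes rest on the binormal model, the Youden rule and 20 to 50% ischaemia, none of which the documents give. AUC 0.70 is itself a planning value, so a single flat figure would claim too much. This is a worthwhile and cheap improvement to a secondary analysis; it does not touch the primary objective.

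**What to change.** In section 9.2, for the comparison with SPECT:

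1. State the rule by which any RFR (and, if intended, FFR) cut-off will be selected, for example the maximum Youden index.
2. Label the data-derived cut-off exploratory. Report it with a bootstrap confidence interval and with bootstrap optimism-corrected sensitivity and specificity, repeating the selection step in every resample.
3. Alongside it, report sensitivity and specificity with confidence intervals at the fixed cut-offs the Background already cites (NHPR ≤0.89, FFR ≤0.80). This is a reporting choice only and implies no view on which threshold should guide care.
4. Make the comparison with the earlier iFR study using the interval for the cut-off as well as its point value.

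Cost: a few sentences in the plan and a short script outside the SPSS menus, with no extra patients or measurements. Reported accuracy will be slightly less favourable, and a residual overstatement of about 0.03 to 0.04 may remain after bootstrap correction, which the report should acknowledge.

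### The power for the SPECT objective is misprinted as 0.90%; read as 90%, it rests on an unstated null AUC and ischaemia share and does not cover FFR versus RFR

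*Combined protocol and SAP*

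**What the plan says.** In section 9.1, the paragraph on the secondary objective, labelled there as the comparison of FFR with RFR, makes three statements:

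- **How the 80 is reached.** About 10–20% of patients are expected to be ineligible for SPECT, and "One Hundred patients with baseline measurements will allow a 20% drop-out to end up with 80 patients" with both SPECT and invasive data.
- **Where the 80 comes from.** A cited iFR study is said to have found that "a sample of 80 patients was necessary to determine the optimal cutoff value of iFR for indicating myocardial ischemia". The number is carried over to RFR because RFR and iFR correlate at 0.99.
- **What the 80 delivers.** It should reach "an area under the ROC curve of 0.70 with 0.90% power at a significance level of 0.05", with a two-sided test.

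Section 9.2 says that the diagnostic performance of RFR against SPECT ischaemia "will be evaluated using receiver operating characteristic (ROC) curve analysis". It names no null value, no method for testing an AUC and no test of two AUCs against each other. Secondary outcome 5 in the Study Objectives section is a comparison of the diagnostic performance of FFR and RFR against SPECT. No section gives an expected proportion of patients with SPECT ischaemia.

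**The concern.** There are three separate difficulties.

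1. The power as printed is impossible. 0.90% is 0.009, below the significance level of 0.05, and a sensible test rejects at least as often as its significance level when the alternative is true. For the primary objective the same section writes power as a proportion, 0.80, so the percent sign is evidently a slip.
2. The intended 90% cannot be checked from the plan. The power of a test on one AUC depends on the null value and on how the patients divide into ischaemic and non-ischaemic. Neither is given. The 0.99 correlation between RFR and iFR says nothing about how many patients in this cohort will have ischaemia.
3. The label does not match the calculation. One target AUC, 0.70, describes one index tested against a fixed value. A comparison of FFR with RFR concerns the difference between two AUCs measured in the same patients.

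What is at stake is how the SPECT results are read. A reader could take the plan to have 90% power whatever the case mix, or to have that power for ranking FFR against RFR. Neither is established.

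**Working it through.** **Inputs from section 9.1:** n = 80; AUC under the alternative A = 0.70; two-sided alpha 0.05 (z = 1.96); power read as 0.90.

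**Inputs assumed because the plan omits them:** null AUC 0.50; share of patients with SPECT ischaemia, varied below.

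**Formulas** (n1 ischaemic, n0 non-ischaemic, n = n1 + n0):

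- Null variance: SE0² = (n + 1) / (12 × n1 × n0)
- Hanley–McNeil alternative variance: SE1² = [A(1 − A) + (n1 − 1)(Qa − A²) + (n0 − 1)(Qb − A²)] / (n1 × n0), with Qa = A/(2 − A) and Qb = 2A²/(1 + A)
- Power = Φ[(0.70 − 0.50 − 1.96 × SE0) / SE1]

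For A = 0.70: Qa = 0.5385, Qb = 0.5765, A² = 0.49, so Qa − A² = 0.0485 and Qb − A² = 0.0865.

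**Step 1: reproduce the plan's figure (50% ischaemia, 40 and 40).**

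- SE0 = √(81 / 19,200) = 0.0650
- SE1 = √[(0.21 + 1.890 + 3.372) / 1,600] = 0.0585
- Power = Φ[(0.20 − 0.1273) / 0.0585] = Φ(1.24) = 0.893

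The total needed for 90% by this formula is 82, and 81 by the Obuchowski binormal variance. The plan's 80 at 90% is therefore reproduced under a null of 0.50 and an even split.

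**Step 2: change only the ischaemia share.**

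- 30% (24 and 56): SE0 = √(81 / 16,128) = 0.0709; SE1 = √(6.081 / 1,344) = 0.0673; power = Φ(0.908) = 0.818
- 20% (16 and 64): SE0 = √(81 / 12,288) = 0.0812; SE1 = √(6.385 / 1,024) = 0.0790; power = Φ(0.518) = 0.698

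**Step 3: change the method.** The plan names none, so the table gives four for n = 80. The alternative-only column puts SE1 in both places. The simulation is binormal, with a DeLong test and 10,000 runs per row.

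| SPECT ischaemia | Hanley–McNeil, null and alternative | Hanley–McNeil, alternative only | Obuchowski, null and alternative | DeLong, simulated |
|---|---|---|---|---|
| 20% | 0.698 | 0.717 | 0.722 | 0.737 |
| 25% | 0.769 | 0.793 | 0.790 | 0.798 |
| 30% | 0.818 | 0.845 | 0.835 | 0.843 |
| 40% | 0.873 | 0.903 | 0.883 | 0.886 |
| 50% | 0.893 | 0.928 | 0.898 | 0.900 |
| 60% | 0.886 | 0.932 | 0.889 | 0.888 |
| 70% | 0.845 | 0.914 | 0.846 | 0.848 |

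A cruder approximation, with the Mann–Whitney null variance under both hypotheses, sits slightly lower: 0.868 at 50%, 0.806 at 30% and 0.693 at 20%. Simulating the Mann–Whitney test gives 0.890, 0.831 and 0.713, so the table's ranges are a fair summary.

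**Step 4: totals for 90% power.** By the first method and the alternative-only method respectively: 82 and 72 at 50% ischaemia, 87 and 80 at 40%, 102 and 95 at 30%, 135 and 131 at 20%.

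**Step 5: the FFR–RFR comparison.** Its power would need an AUC for each index and the correlation between the two estimated AUCs. The plan gives one AUC and no difference to detect, so no power for this comparison can be computed from it.

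**The case against.** The strongest reply is that little is wrong beyond a percent sign. The 90% is reproduced at an ordinary case mix, and the primary paragraph's 0.80 shows how the figure was meant. The cited iFR study may supply the ischaemia share, but it is not among the documents. The objective is secondary and enrolment is unaffected. Most of this stands. What remains is that the plan's own text does not give the inputs that the figure depends on, and that it places the figure under a comparison which the figure does not address.

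A reader might draw four stronger conclusions that the documents do not support:

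- **That 90% holds only at an even split, or is a best case.** This depends on the formula. With the alternative-only variance, power is at least 0.90 from 40% to 70% ischaemia and peaks at about 0.93.
- **That ischaemia will be uncommon, so the analysis is underpowered.** No section gives a rate. The nearest figures are the assumed FFR mean of 0.82 and SD of 0.08 in section 9.1. If FFR is normal, Φ(−0.25) = 40% of values lie at or below 0.80, and Φ(0.125) = 55% at or below the 0.83 cut-off that the Background reports for aortic stenosis. FFR positivity is only a proxy for SPECT ischaemia, so this settles nothing, but it does not point to 20–30%.
- **That no patient may be lost beyond the 20%.** This is true only at the upper end of the stated 10–20% SPECT ineligibility. At 10%, 90 patients remain and ten further losses are covered.
- **That the iFR study's assumption was missing or unfavourable.** The study is not available here, so this cannot be said.

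**Conclusion.** The point holds as a misprinted power plus undisclosed assumptions. It is not an error in the number 80. As printed, the power is impossible; as 90%, it is reproduced for one AUC of 0.70 against 0.50, two-sided 0.05, when roughly 40–60% of the 80 have SPECT ischaemia (about 0.87–0.93 by method). It drops to about 0.82–0.85 at 30% and 0.70–0.74 at 20%.

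The conclusion rests on two assumptions that the plan does not state: a null AUC of 0.50 (a higher null would need more patients) and an ischaemia share, for which only a range can be shown. Under either, the figure is not a power for FFR against RFR. The primary objective is untouched. The correction should be made, because the stated figure is wrong as it stands and cannot be verified as intended.

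**What to change.** Replace the power sentence in section 9.1 with wording such as: *80 patients give about 90% power to show that an RFR AUC of 0.70 exceeds 0.50 (two-sided 0.05) if about half have SPECT ischaemia, about 82–85% at 30% and 70–74% at 20%; this is not the power for a difference between FFR and RFR.* Name the method used. If one formula is chosen, give its single values in place of the ranges. If the cited iFR study supplied the ischaemia share, state that share.

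The cost is about two sentences. A stated secondary power becomes conditional and slightly less favourable. Enrolment and the primary analysis do not change.
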